## **6. Statistical analysis**

This small pilot trial aims to test prototype HT devices and evaluate their safety and feasibility in patients with PAD. The main goal is to gather initial data to refine device design and guide the development of future large-scale studies. Due to the exploratory nature of this trial, no power analysis was performed. Changes in each outcome from baseline to the 12-week follow-up will be compared using paired two-sample t-tests. A two-sided P value of  $<.05$  will be regarded as statistically significant. Before starting the intervention, participants will undergo a supervised HT session, during which skin temperature and blood pressure will be monitored every 5 minutes throughout the 90-minute session. Skin temperature and blood pressure responses during this session will be analyzed using repeated-measures analysis of variance. When a significant main effect is found, Sidak multiple comparisons tests will evaluate differences between time points relative to baseline. A P value of  $<.0028$  will be considered statistically significant for the Sidak-adjusted comparisons. All statistical analyses will be conducted using Prism 10 (Version 10.3.0 (461)).

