## **2. Objectives**

The primary goal of this study is to design a clinical-grade, easy-to-use leg HT system for elderly individuals suffering from PAD. Building on an existing cryotherapy water-circulating device designed for sports recovery, we will develop a new prototype system consisting of leg sleeves composed of an inner layer of polyurethane water-circulating pads and an outer layer of six inflatable bladders. The feasibility and safety of the prototype units will be evaluated in a single-arm pilot trial involving six patients with symptomatic PAD. The primary outcomes are completion rates, safety, and device usability. Secondary outcomes included changes in 6-minute walk distance, calf strength, performance on the five times sit-to-stand test, and quality of life as measured by the Walking Impairment Questionnaire (WIQ).

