## **4. Experimental protocol**

Participants will attend two baseline laboratory visits. Before each session, they will be instructed to fast overnight, avoid exercise for 24 hours, and refrain from smoking for 4 hours. During the first visit, participants will receive informed consent, complete a medical history form, have their leg symptoms assessed using the San Diego Claudication Questionnaire, complete the Mini-Mental Status Examination, and undergo a thermal sensation test with heating pads on their thighs and calves. The ABI will be assessed following American Heart Association guidelines. After a 10-minute rest, a handheld Doppler ultrasound probe will be used to measure systolic pressures in the posterior tibial, dorsalis pedis, and brachial arteries. The ABI for each leg will be calculated

by dividing the average dorsalis pedis and posterior tibial pressures by the average brachial pressures. Participants will then be familiarized with the 6-minute walk test, isokinetic calf strength testing, and the five-times sit-to-stand test.

The second visit, conducted at least 48 hours later, will include (1) blood pressure measurement, (2) a 6-minute walk test, (3) torque assessments of the plantar flexors using an isokinetic dynamometer, (4) the five-times sit-to-stand test, and (5) quality of life assessment via the WIQ. After completing baseline tests, participants will undergo a supervised 90-minute treatment session with the prototype HT device to monitor acute changes in skin temperature and blood pressure. Thermocouples (MLT422; AD Instruments, Colorado Springs, CO) will be taped to the calf and thigh to measure leg skin temperature, and systolic and diastolic blood pressures will be recorded every 5 minutes.

Participants will be given the prototype device for daily use while lying down or seated with legs extended. They will log therapy sessions and measure blood pressure before and after each session using a portable monitor (Omron 3 Series Upper arm, Omron Healthcare Co. Ltd., Kyoto, Japan). Weekly check-ins with the study coordinator will track therapy dates, times, blood pressure readings, and any adverse effects. Outcomes will be reassessed at the end of the 12-week intervention, with participants stopping treatment 48 hours before the final evaluations to isolate chronic effects.

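### The acute-session comparisons with baseline should not depend on a significant repeated-measures F test: the Sidak adjustment already controls error, and the gate costs power

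*Combined protocol and SAP*

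**What the plan says.** Section 2 (Objectives) describes a "single-arm pilot trial involving six patients with symptomatic PAD". Under Section 4 (Experimental protocol), after the baseline tests, "participants will undergo a supervised 90-minute treatment session with the prototype HT device to monitor acute changes in skin temperature and blood pressure", and "systolic and diastolic blood pressures will be recorded every 5 minutes". Section 6 (Statistical analysis) repeats the schedule: "skin temperature and blood pressure will be monitored every 5 minutes throughout the 90-minute session".

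The analysis has two stages. First: "Skin temperature and blood pressure responses during this session will be analyzed using repeated-measures analysis of variance". Then: "When a significant main effect is found, Sidak multiple comparisons tests will evaluate differences between time points relative to baseline". The general two-sided threshold is .05. Section 6 sets a separate threshold of .0028, below which a P value "will be considered statistically significant for the Sidak-adjusted comparisons".

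Section 6 does not say whether a sphericity correction is applied, or whether the comparisons use the pooled ANOVA error or a separate error for each pair. It plans no estimate or confidence interval for this session, and it states that the trial is exploratory and that power was not calculated.

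**The concern.** The gate and the comparisons ask different questions. The comparisons ask whether each heated reading differs from baseline. The gate asks whether there is any difference among 19 time points, on 18 numerator degrees of freedom. If blood pressure changes early and then stays level, the 18 heated readings resemble each other and only baseline stands apart. The F test spreads that single contrast over 18 degrees of freedom and can miss a change that the comparisons would have found.

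A gate of this kind is defensible when the second-stage tests do not control the family error themselves. Sidak comparisons do. With six people there is little power to spare, and this session is the only blood-pressure response analysed before the device goes home. If the gate stays shut, the plan provides no other formal result for the session.

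**Working it through.** **The plan's own figure.** Readings every 5 minutes over 90 minutes give 90/5 = 18 readings after baseline, so 19 time points and 18 comparisons (the count is derived, not stated). The Sidak per-comparison level is 1 − (1 − 0.05)^(1/18) = 0.002846, which rounds to .0028. With 17 or 19 comparisons it would be .0030 or .0027. The threshold therefore reproduces, and it confirms that the family is 18 comparisons with baseline. I read .0028 as applying to unadjusted P values.

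**Closed-form check of the dilution.** Take n = 6, 19 time points, independent readings and an immediate sustained change of d within-person SDs. The noncentrality is λ = n·d²·18/19. For d = 1.5, λ = 6 × 2.25 × 18/19 = 12.79. The F test on 18 and 90 df then has 47% power. A one-df contrast of baseline against the mean of the later readings has 81%.

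**Inputs for the simulation.** From the documents: six people, 19 readings, omnibus level .05, per-comparison level .002846. Assumed, because the documents give none: within-person SD 6 mmHg, AR(1) correlation 0.5, a 10 mmHg fall (10/6 = 1.67 SD), and four shapes. An ungated success is any of the 18 comparisons below .002846. A gated success also requires F to be significant at .05.

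| Shape of a 10 mmHg fall | Pooled error, uncorrected F: ungated vs gated | Loss (points) | Per-comparison error, Geisser-Greenhouse F: ungated vs gated | Loss (points) |
|---|---|---|---|---|
| Abrupt, sustained | 92% vs 61% | 31 | 71% vs 10% | 61 |
| 15-min build-up | 90% vs 75% | 15 | 63% vs 22% | 41 |
| 30-min build-up | 89% vs 83% | 6 | 58% vs 32% | 26 |
| Linear over 90 min | 68% vs 65% | 3 | 34% vs 21% | 13 |

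Repeat runs of 6,000 to 20,000 replicates agree with these figures to within 2 points. A gate cannot raise the chance of a finding, so the sign of the loss is certain; only its size depends on the assumptions.

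**Sensitivity to the size of the fall.** With pooled error and an uncorrected F, a 15 mmHg abrupt fall gives 99.9% vs 97%. In SD units, with independent readings and an abrupt fall, the figures are 48% vs 19% at 1 SD and 98% vs 78% at 2 SD, and the loss is 0.4 points at 3 SD. With Geisser-Greenhouse and separate paired comparisons, the losses are 31 points at 1 SD, 64 at 2 SD and still 16 at 3 SD.

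**Family error without the gate, no true change.** It is 3.0% to 5.6% for AR(1) 0 to 0.7. At AR(1) 0.8 it is 7.1% with pooled error (5.8% with the gate) and 4.2% with per-comparison error.

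**A single summary in place of time points.** The per-person mean of heated readings minus the pre-heating value detects the abrupt 10 mmHg fall about 89% of the time, but the linear fall only 39% of the time.

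**The case against.** Three stronger readings are tempting, and the documents support none of them.

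- **That the session is looking for a sustained fall, so the F test is the wrong test for its purpose.** Section 4 speaks only of acute changes and gives no direction, size or shape. An abrupt sustained fall is a plausible pattern, and it is also the one that most disadvantages an omnibus test.
- **That a real fall would be reported as no effect.** Section 6 leaves the comparisons unrun. It does not say how a non-significant F is to be described, and it does not forbid showing means.
- **That the F test is weak in general.** With an uncorrected F and a gradual fall, the gate costs 3 to 6 points, and at 15 mmHg almost nothing even for an abrupt fall. The largest loss in the table needs a Geisser-Greenhouse correction and separate error terms, and Section 6 specifies neither. It does not exclude them either.

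It is also fair to say that little rests on this P value. The primary outcomes are completion, adverse events and usability. Readings are taken under supervision, participants measure blood pressure around every home session, and no decision in the plan turns on the F test.

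These points limit the size and importance of the concern. They do not justify keeping the condition, which gives almost no error control beyond what the Sidak adjustment already supplies.

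**Conclusion.** The point holds in a limited form. The gate is in the text, is not needed for error control at moderate correlation, and loses power for every shape examined. Under the stated assumptions and a 10 mmHg fall, the loss runs from 3 to 31 points with an uncorrected F and pooled error, and from 13 to 61 points with a Geisser-Greenhouse F and per-comparison error. It largely disappears at about 15 mmHg if F is uncorrected. All these sizes rest on an assumed SD, correlation, effect and shape.

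One qualification: with pooled error and strong autocorrelation, the ungated family error goes above 5% (about 5.6% at AR(1) 0.7, 7.1% at 0.8).

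The change is worth making because it is cheap. The importance is modest.

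**What to change.** In Section 6, delete the opening condition of the sentence on the Sidak tests. State that all 18 comparisons with baseline will be reported whatever the F test shows, with the mean change from baseline and its 95% CI at each time point. The F test may still be reported alongside.

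In the same edit, state whether a sphericity correction is used and which error term the comparisons take. Per-comparison error keeps the family error below 5% under strong autocorrelation but has less power (71% against 92% for the abrupt fall, ungated).

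A per-person mean of heated readings minus the pre-heating value, with a 95% CI, can be added for systolic and diastolic pressure as a supplementary summary. It should not replace the time-point comparisons, because it is weak for a gradual change.

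The cost is a few sentences in Section 6 and no new data. The only statistical price is the slight excess in family error noted above, if pooled error is used and autocorrelation is strong.

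### Step-down Holm-Sidak would keep every finding of the planned, valid single-step Sidak comparisons with baseline (fixed P<.0028), sometimes add more, and stay within the same 5% family-wise allowance

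*Combined protocol and SAP*

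**What the plan says.** Section 4 (Experimental protocol) describes one supervised session before home use, in which "systolic and diastolic blood pressures will be recorded every 5 minutes". Section 6 adds that "skin temperature and blood pressure will be monitored every 5 minutes throughout the 90-minute session". The responses go into a repeated-measures analysis of variance. "When a significant main effect is found", "Sidak multiple comparisons tests will evaluate differences between time points relative to baseline". The decision rule follows: "A P value of $<.0028$ will be considered statistically significant for the Sidak-adjusted comparisons".

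Section 2 (Objectives) describes a "single-arm pilot trial involving six patients with symptomatic PAD". The plan does not write out the number of comparisons, mentions no step-down ordering, and gives no reason for one fixed cut-off.

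**The concern.** A single cut-off for every comparison is the single-step form of Sidak. Strictly, that bar is needed only for the smallest of the 18 P values. Once that hypothesis is rejected, 17 remain, and the next P value can be judged against a slightly easier bar without breaching the family-wise 5%.

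If 90 minutes of heating produces a sustained change, many consecutive readings will differ from baseline together, and a fixed bar then gives up power. With six people, power is scarce, and this session is the only acute response that section 6 plans to analyse. At stake is how many readings are reported as changed. No primary outcome is affected.

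**Working it through.** **Inputs from the plan**
- Readings every 5 minutes for 90 minutes (sections 4 and 6): 90/5 = 18 after baseline, plus one at time 0. The 18 is inferred.
- Cut-off P<.0028 (section 6).
- Family-wise level .05. Section 6 states .05 for the 12-week tests; .0028 with 18 comparisons implies the same level here.
- Six patients (section 2).

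**Assumptions (not in the plan)**
- Within-person SD 6 mmHg; AR(1) correlation 0, .5 or .8 between readings.
- A fall that builds over 30 minutes and then holds.
- Either the pooled ANOVA error (90 df) or a separate error for each comparison (5 df). The plan does not say which.

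**Step 1: reproduce .0028.** Single-step Sidak gives 1-(1-.05)^(1/18) = .002846, which rounds to .0028. Seventeen comparisons give .0030 and nineteen give .0027, so 18 fits. Bonferroni, .05/18 = .002778, also rounds to .0028, but the plan names Sidak.

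**Step 2: step-down thresholds.** Order the unadjusted P values and compare the i-th smallest with c(i) = 1-.95^(1/(19-i)):

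| i | 1 | 2 | 9 | 14 | 17 | 18 |
|---|---|---|---|---|---|---|
| c(i) | .00285 | .0030 | .0051 | .0102 | .0253 | .05 |

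**Step 3: what follows without any assumption on effects.** The first threshold is the planned bar and later ones only rise. So every P value below the planned bar is also rejected by the step-down procedure. Step-down makes a rejection only if the smallest P value passes c(1), exactly as single-step does. When nothing changes, the chance of any false finding is therefore identical. The one difference is rounding: with 18 independent tests, .0028 gives 1-(1-.0028)^18 = .0492 rather than .05.

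**Step 4: size of the gain.** Mean number of the 18 readings declared, simulated without the preliminary F test:

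| Fall | Error | Correlation | Single-step | Step-down |
|---|---|---|---|---|
| 6 mmHg (1 SD) | pooled | 0 | 1.4 | 1.6 |
| 10 mmHg | pooled | 0 / .5 / .8 | 6.1 / 7.0 / 9.3 | 7.3 / 8.1 / 10.5 |
| 10 mmHg | separate | 0 / .5 / .8 | 1.7 / 1.7 / 2.1 | 2.0 / 2.1 / 2.8 |
| 15 mmHg | separate | 0 / .5 / .8 | 4.9 / 4.9 / 5.9 | 6.7 / 6.7 / 8.3-8.5 |

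No single-step rejection was lost in any of these runs.

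**Step 5: where the gain falls.** At 10 mmHg, pooled error, correlation 0, power rises by about 6 points at the 5-25 minute readings (10% to 16%) and about 7 points on the plateau. At 15 mmHg with separate errors, correlation 0, the gains are 6.7 and 10.4 points. Concentration at onset appears only for larger effects with pooled error. In simulations with the F test applied first and correlation 0, a 3 SD plateau gave 32% to 57% at 15 minutes but 98% to 99% on the plateau.

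**Step 6: error when some readings change.** With no change for 30 minutes and then a 12 mmHg fall, the chance of a false finding among the unchanged readings was about 1.0-1.7% for single-step and 2.1-3.0% for step-down. With a 30 mmHg fall, step-down reached 4.4-4.6% in repeated runs, still below 5%.

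**Side finding.** When nothing changes, pooled error at correlation .8 gave 7.1% for both procedures alike. That concerns the error term and does not separate the two methods.

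**The case against.** The planned procedure is pre-specified, valid and controls the family-wise error. The acute session responses are not among the listed primary outcomes, and section 6 calls the trial exploratory. On this view the point is a preference. That stands as a limit on its weight.

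Four stronger readings are tempting, and none is supported.

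- **That single-step Sidak is an error.** It is not. It is only less powerful than an available alternative.
- **That its strictness buys no error control.** This is true only when nothing changes. Under a partial change the step-down version roughly doubles the false-finding rate at 12 mmHg, though it stays within 5%. The extra false findings fall on unchanged readings. If those come early, onset can be placed too soon.
- **That early readings suffer most, so onset is reported late.** At 10 mmHg with pooled error the gain is similar at onset and on the plateau. The median first-declared reading is the same under both methods (30, 30 and 25 minutes for the three correlations), although among runs with any declaration the average is about 3 minutes earlier. Power at the 5-25 minute readings is still only 16-25% after the change.
- **That the comparison holds however .0028 is read.** Section 6 says the cut-off "will be considered statistically significant for the Sidak-adjusted comparisons". Applied to already adjusted P values, it would make the family-wise level .0028, an unadjusted bar of about .00016 (1-(1-.0028)^(1/18)). Step-down at .05 would then not have the same false-finding rate. The match of .0028 with 1-.95^(1/18) favours the unadjusted reading, but the wording does not settle it.

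It is also fair to object that ordinary 95% intervals may exclude zero at readings Holm-Sidak does not declare. Clear labelling deals with this.

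**Conclusion.** The point holds as a modest gain in efficiency over a sound method. Two parts are exact, given 18 comparisons and .0028 as a bar for unadjusted P values: no planned rejection is lost, and the chance of any false finding when nothing changes is the same.

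The size rests on assumed effects. The gain is about 0.2 of a reading at 1 SD (pooled error, correlation 0), 0.3 to 0.7 at 10 mmHg with separate errors, and about 1 to 2.5 at 10 mmHg pooled or 15 mmHg separate. For very large changes it vanishes on the plateau. The price is fuller use of the 5% allowance when only some readings change. Staying below 5% is a result of the partial-change runs made here, and both methods depend equally on a suitable error term.

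**What to change.** In section 6, replace the Sidak sentence and the fixed .0028 with:

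> The 18 comparisons with baseline for each response will use the Holm-Sidak step-down procedure at a family-wise level of .05. Ordered unadjusted P values are compared with 1-.95^(1/(19-i)), i = 1 to 18, stopping at the first that fails.

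Add that the mean change at each reading will be reported with a 95% confidence interval labelled as unadjusted and not used to declare significance.

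The wording also removes the doubt over adjusted and unadjusted P values. It needs no new data, and the procedure can be computed directly from the 18 unadjusted P values. What is given up is a matching set of simultaneous confidence intervals, which single-step Sidak could supply. If the trial team wants those, keeping the planned method is defensible, provided the plan states that .0028 applies to unadjusted P values.
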